#### Note:

Medications are coded using WHO Drug dictionary version March 2016.

## 4.8 Safety Analysis

### 4.8.1 Adverse Events

Summaries of adverse events are described above.

### 4.8.2 Body Weight and Temperature

Body weight and temperature, recorded prior to vaccination, will be listed.

### 4.8.3 Physical Examination

Results from physical examination will be listed.

## 4.9 Adjustment for Covariates

The complete set of covariates that will be used to calculate the adjusted GMT ratio will include treatment group (2 treatments), pre-vaccination mean GMT titer (value), age strata (2 categories, 6 through 35 months or 36 through 59 months), gender (male or female), influenza vaccination received prior year (Yes or No), number of doses (1 or 2) and investigator site (site identifier) as described in [Section 4.7.2](#).

## 4.10 Protocol Deviations

Major protocol deviations (major deviations, see [Section 4.10.1](#)) will be listed, even if they are assessed not to influence any of the immunogenicity or safety results for subjects who have been entered into the study and assigned a subject number.

The following criteria will exclude a subject from the evaluable population. These will be listed in the deviation listing:

- Not provided both pre- and post-vaccination blood samples
- Laboratory-confirmed influenza infection during the active period (Day 1 to Exit Visit)
- Received prohibited medication during the active study period which medically assessed to potentially impact immunogenicity results

**Note:** Other reasons for deviation may be added to this list, but will be done prior to unblinding of the study. The reasons highlighted will be used in defining the evaluable population and per-protocol population.

### 4.10.1 Protocol Deviations Definitions and Procedure

Deviations from the protocol will be documented on an ongoing basis by the study monitors and lead clinical research associate or designee throughout the study period.

At the time of database lock, prior to unblinding and while the major protocol deviations are being reviewed, the project manager or designee will forward all relevant documentation highlighting protocol deviations to the study statistician. These deviations will be included in the protocol deviation document for agreement and will be listed with the protocol deviations in the clinical study report (CSR).

*Major protocol deviations* are deviations that could significantly affect the subject's safety, rights, or welfare and/or significantly impact the completeness, accuracy and reliability of the study data. Examples of major protocol deviations include:

- enrolling subjects in violation of inclusion/exclusion criteria defined in the protocol,
- failing to collect pre-vaccination or post-vaccination blood samples
- Subject took prohibited medication during active period (Day 1 to Exit Visit) in the study;
- Administration of second dose of study vaccine when contraindicated as described in the protocol;
- Failure to obtain written Informed Consent from a parent/legal guardian prior to initiating study procedures
- Blood sample handling issues which would affect immunogenicity results e.g. samples freeze/thawed; samples not processed within allowed time frames;
- Failure to report a SAE to Seqirus within timeframe specified in the protocol;

- Subject received an Investigational product which had significant temperature deviations outside pre-specified range in the protocol

*Minor protocol deviations* are deviations that do not significantly affect the subject's safety, rights, or welfare and/or significantly impact the completeness, accuracy and reliability of the study data. Examples of minor protocol deviations include:

- a blood sample not being drawn at an interval specified by the Study Protocol;
- Subject Lost to follow-up;
- Randomization errors which did not affect immunogenicity results or compromised subjects safety;
- Subject completed e-diary outside of allowed time window;
- Missed study procedures with the exception of pre-vaccination and/or post-vaccination blood samples;
- Subject failed to complete and/or submit e –diary (solicited and/or unsolicited);
- Study procedures outside allowed time window;
- Study visit outside allowed time window;
- Safety follow up phone call missed/outside allowed time window;
- Subject's initials missing/ boxes checked instead of initialled, corrections not initialled/dated: MINOR if corrected at following subject visit; MAJOR if not corrected;
- Subject did not complete "time" field on ICF;
- Discrepancies between ICF time and source document time;

Protocol deviation listings will be reviewed by Seqirus prior to the finalisation of the population datasets, which will occur prior to unblinding. The list will be used to determine which subjects should be excluded from either the Evaluable or the Per Protocol Population.

#### **4.11 Missing Values – Missing Visits**

Titer values recorded as <10 will be summarised as 5.

When solicited AEs occur, if entries are missing for only some of the days, then the intensity will be imputed as the maximum of the previous and next non-missing value for calculation of the aggregated value.

#### **4.12 Deviations from SAP**

Any deviations from the original statistical plan will be described and justified in the final CSR, whether written post interim or final analysis.

### 4.13 Changes in Conduct or Planned Analyses from the Protocol

The term 'sex' has been replaced with 'gender' throughout the analysis section. The safety population has been refined for overall, solicited safety, solicited safety after 1st vaccination and solicited safety after 2nd vaccination.

The term Number of Doses (1 vs 2) has been included as an additional covariate in the GLM model fitting.

There will be no separate summary tables for SAEs by maximum intensity and relationship, discontinuations due to AEs related to Study Vaccine, or discontinuations due to SAEs. These details will be in listings only.

Unsolicited AEs will be presented overall and not after each vaccination dose, as stated in the secondary endpoints. The wording in the endpoint should have been 'Frequency and severity of unsolicited AEs for at least 28 days (ie, day of vaccination and 27 subsequent days) after the last vaccination dose'.

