1.3 STUDY OVERVIEW

The present study is a phase 3, randomized, multicenter, observer-blinded study to evaluate the immunogenicity and safety of Seqirus QIV in comparison with a US-licensed 2016-2017 quadrivalent influenza vaccine (Comparator QIV) in children 6 months through 59 months of age. Seqirus QIV is intended for active immunization against influenza disease caused by influenza virus subtypes A and types B present in the vaccine. In the US, routine annual influenza vaccination of all persons 6 months of age and older continues to be recommended [[Centers for Disease Control and Prevention, 2013](#)].

The study will be conducted during the 2016-2017 Northern Hemisphere influenza immunization season in male and female children 6 months through 59 months of age. Subjects will be randomized to either treatment group in a 3:1 ratio (Seqirus QIV: Comparator QIV). The randomization will be stratified by age stratum into two study cohorts (Cohort A: 6 months through 35 months of age, and Cohort B: 36 months through 59 months of age). Age stratification will employ a quota to ensure that no more than 60% of the total sample subjects are represented in each age stratum. An interactive response technology (IRT) system will be used for subject randomization.

Subjects will receive either one or two doses of Study Vaccine (Seqirus QIV or Comparator QIV) as clinically indicated, depending on their previous history of influenza virus vaccination, in accordance with influenza vaccination dose recommendations of the US Advisory Committee on Immunization Practices (ACIP) for Prevention and Control of Seasonal Influenza with Vaccines. See [Section 3](#) for more information on the ACIP recommendations, dose and dosing regimen.

Immunogenicity assessment will occur prevaccination, and approximately 29 days after the last study vaccination dose by serological assessment with the hemagglutination inhibition (HI) assay. Safety monitoring will include solicited local reactions and systemic adverse events (reactogenicity) for 7 days following each study vaccination dose; unsolicited adverse events for at least 28 days following the last study vaccination dose; and cellulitis-like reactions for at least 28 days following the last study vaccination dose. Serious adverse events monitoring will continue for 180 days following the last study vaccination dose.

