2.2.2 Secondary Endpoints

Secondary Safety Endpoints:

- Frequency and severity of solicited local reactions and systemic adverse events (AEs) for 7 days after each vaccination dose;
- Frequency of cellulitis-like reactions for at least 28 days after each vaccination dose;
- Frequency and severity of unsolicited AEs for at least 28 days after each vaccination dose;
- Frequency of serious adverse events (SAEs) for at least 180 days after the last vaccination dose.

Secondary Immunogenicity Endpoints:

The humoral immune response will be assessed in terms of HI antibodies for both the Seqirus QIV and Comparator QIV. Serum HI antibody titers against the 4 influenza vaccine strains will be used to calculate:

- Geometric mean titer (GMT): Geometric mean of HI titers prevaccination (Day 1) and postvaccination (Study Exit Visit);
- Seroconversion rate: Percentage of subjects with either a prevaccination HI titer $< 1:10$ and a postvaccination HI titer $\geq 1:40$ or a prevaccination titer $\geq 1:10$ and a ≥ 4 -fold increase in postvaccination titer;
- The percentage of subjects with a titer ≥ 40 (seroprotection rates) at Day 1 and Study Exit Visit;
- Geometric Mean Fold increase (GMFI)***: Geometric mean-fold-titer rise from Day 1 to Study Exit Visit.

***The rate of seroprotection is defined as the proportion of subjects with an HI titer $\geq 1:40$.

****GMFI in antibody titer is defined as the geometric mean of the fold increase of postvaccination HI antibody titer over the prevaccination HI antibody titer.

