10.3 SAFETY ASSESSMENTS

Safety will be assessed through solicited local reactions, solicited systemic AEs, unsolicited AEs and SAEs.

Type, frequency and intensity of solicited local reactions through to Day 7 (Day 1, 2, 3, 4, 5, 6, 7) following each study vaccination dose. These include pain, induration/swelling, and erythema/redness.

Frequency of cellulitis-like reaction for 28 days following vaccination. Cellulitis-like reaction is defined as the concurrent presence of grade 3 injection site pain, erythema/redness and induration/swelling.

Type, frequency, duration and intensity of solicited systemic AEs through to Day 7 (Day 1, 2, 3, 4, 5, 6, 7) following each study vaccination dose. These include headache, malaise and fatigue, myalgia, fever, diarrhea, and nausea and/or vomiting for children 36 months through 59 months of age, and fever, diarrhea, nausea and/or vomiting, loss of appetite, and irritability for children 6 months through 35 months of age.

Frequency of antipyretic use in the 7 days after each vaccination dose.

Type, frequency, duration and intensity of unsolicited AEs for at least 28 days following each study vaccination dose.

Frequency of SAEs and AESIs for at least 180 days following vaccination.

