11.3.2.2 Secondary Analyses

Secondary Objectives:

The secondary objectives of the study are:

1. To assess the safety and tolerability of Seqirus QIV, in two age strata: 6 months through 35 months and, 36 months through 59 months of age, as well as overall.

2. To characterize the immunogenicity of Seqirus QIV and the US-licensed comparator QIV in two age strata: 6 months through 35 months and, 36 months through 59 months, as well as overall.

Secondary Endpoints:

Secondary safety endpoints:

AEs will be monitored after vaccination as per the following;

- Frequency and severity of solicited local adverse reactions and systemic adverse events (AEs) for 7 days (ie, day of vaccination and 6 subsequent days) after each vaccination dose;
- Frequency of cellulitis-like reaction for at least 28 days after each vaccination dose;
- Frequency and severity of unsolicited AEs for at least 28 days (ie, day of vaccination and 27 subsequent days) after each vaccination dose;
- Frequency of serious adverse events (SAEs) for 180 days after the last vaccination dose.

For all solicited AEs the following summaries will be presented by treatment group overall and by age stratum:

- The number and percentage of subjects reporting at least one occurrence of each type of adverse event will be presented with 95% CIs.
- The number and percentage of subjects experiencing at least one local reaction will be presented with 95% CIs.
- The number and percentage of subjects experiencing at least one systemic adverse event will be presented with 95% CIs.

For each of these summaries the relative risk and 95% CIs will be presented for Seqirus QIV/Comparator QIV.

All summaries will be presented overall and by maximum intensity. Analyses will be repeated by sex and by race/ethnicity where specified.

Unsolicited AEs will be coded using the current version of the Medical Dictionary for Regulatory Activities (MedDRA). The number (and percentage) of subjects experiencing at least one event (ie, the incidence) of unsolicited AEs will be summarized by body system overall and by maximum intensity. All summaries will be presented by treatment group overall and by age stratum. Analyses will be repeated by sex and by race/ethnicity where specified.

Summaries will be presented for:

- Any AEs
- Any AEs by maximum severity

- Any AEs by relationship to Study Vaccine
- Any SAEs
- Any SAEs by maximum severity
- Any SAEs by relationship to Study Vaccine
- Any discontinuations due to AEs

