#### **4.7.4 Secondary Endpoints - Safety**

AEs will be monitored after vaccination as per the following;

- Frequency and severity of solicited local adverse reactions and systemic adverse events (AEs) for 7 days (ie, day of vaccination and 6 subsequent days) after each vaccination dose;
- Frequency of cellulitis-like reaction for at least 28 days after each vaccination dose;
- Frequency and severity of unsolicited AEs for at least 28 days (ie, day of vaccination and 27 subsequent days) after each vaccination dose;
- Frequency of serious adverse events (SAEs) for at least 180 days after the last vaccination dose.

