All the AEs starting on the day of or before the exit visit (Day 29 + 4) will be included in the summaries of unsolicited AEs. AEs starting after the exit visit will be included in the subject listings and flagged but not included in the above summaries. Where an AE start date is partially or fully missing, and it is unclear as to whether the AE starts prior to the exit visit, it will be assumed that it does.

In the interim analysis, SAEs started after the exit visit will be excluded from the analysis. SAEs up to day of the safety follow-up call, irrespective of the date will be included in the final safety analysis.

If sufficient numbers of cases of AEs occur, more formal statistical analyses of event rates, duration or severity may be conducted.

Deaths will be presented by time period (Day 1 to Study Exit Visit, and Day 1 to Day 180 after last vaccination dose), by treatment, subject number, preferred term, and relationship.

All other AE information collected (e.g. outcome, action taken) will be listed as appropriate.

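### SAP 4.13 misdescribes the unsolicited AE window, and no planned table shows the protocol's per-dose unsolicited AE endpoint

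*SAP*

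**What the plan says.** Protocol 2.2.2 lists as a secondary safety endpoint "Frequency and severity of unsolicited AEs for at least 28 days after each vaccination dose". Protocol 10.3 asks for the same reference point: "Type, frequency, duration and intensity of unsolicited AEs for at least 28 days following each study vaccination dose". Protocol 11.3.2.2 repeats it in the analysis section. SAP 2.2.2 keeps *each*, and so does SAP 4.7.4: "Frequency and severity of unsolicited AEs for at least 28 days (ie, day of vaccination and 27 subsequent days) after each vaccination dose".

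SAP 4.13, the section for changes from the protocol, departs from this: "Unsolicited AEs will be presented overall and not after each vaccination dose, as stated in the secondary endpoints". It supplies the wording it says the endpoint should have had: "unsolicited AEs for at least 28 days (ie, day of vaccination and 27 subsequent days) after the last vaccination dose". It gives no other reason.

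SAP 4.7.4.4 holds the counting rule. An unsolicited AE enters the summaries if it begins after exposure to study vaccine. The closing limit is: "All the AEs starting on the day of or before the exit visit (Day 29 + 4) will be included". SAP 5.3.3 lists unsolicited AE tables overall and by age stratum, gender, race, ethnicity, relationship and intensity. None is by dose.

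**The concern.** An endpoint definition should tell the reader which events a table contains. Here the section that announces the change describes a 28-day period tied to the last dose, the endpoint sections describe a period after each dose, and the programming rule runs from first exposure to exit. A programmer or report author who works from 4.13 would describe the tables wrongly.

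The second matter is the result itself. The protocol asks for unsolicited AEs after each dose. The SAP keeps by-dose summaries for solicited AEs (4.7.4.2), cellulitis-like reactions (4.7.4.3) and antipyretic use (4.7.5), but not for unsolicited AEs. In young children, some receiving two doses, whether events arise mainly after the first or the second exposure is an ordinary safety question, and the planned tables do not answer it.

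**Working it through.** The plan states no figure on this point, so the check is a comparison of texts with day counts from the visit windows.

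**1. Inputs**
- Dose 2, if scheduled: Day 29 + 4, so 28 to 32 days after dose 1 (SAP 3.3.2).
- Exit Visit, one-dose schedule: Day 29 + 4 (SAP 3.3.3).
- Exit Visit, two-dose schedule: 28 + 4 days after dose 2 (SAP 3.3.3).

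**2. Follow-up pooled in one table**
- One-dose child: 28 to 32 days from vaccination to exit.
- Two-dose child: 28 + 28 = 56 to 32 + 32 = 64 days.
- Ratio: 56/28 = 64/32 = 2.

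The share of two-dose children, *f*, is not in the documents. With minimum windows, mean follow-up behind a pooled percentage is 28(1 − *f*) + 56*f* = 28(1 + *f*) days. For assumed shares of 10%, 50% and 90% this gives 30.8, 42.0 and 53.2 days.

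**3. Does any listed table separate the doses?**
The age-stratum tables do not, because both cohorts receive one or two doses (SAP 3.2). The other breakdowns do not involve dose. The AE listing (16.2.7.1) is by subject and is not a summary.

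**4. How far apart are the texts for a two-dose child?**
Count calendar days with dose 1 on Day 1. Dose 2 falls on Day 29 to 33. Exit falls between Day 29 + 28 = 57 and Day 33 + 32 = 65.
- Rule in 4.7.4.4, first exposure to exit: 57 to 65 days.
- *Each* dose, day of vaccination plus 27: 28 + 28 = 56 days. This is 57 − 56 = 1 to 65 − 56 = 9 days short of the rule, and the phrase for at least 28 days allows for that gap.
- *Last* dose with the parenthesis in 4.13 taken at face value: 28 days. This is 57 − 28 = 29 to 65 − 28 = 37 days short of the rule.

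The *each* wording and the counting rule therefore cover nearly the same period. The 4.13 wording is the one out of line. The 29 to 37 days measure how far that wording misdescribes the analysis; they are not days of data that will be lost.

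**The case against.** A reader might infer from 4.13 that the whole dose 1 period of two-dose children will be dropped. The documents do not support that. The same paragraph says that unsolicited AEs are presented overall, 4.7.4.4 counts from exposure, and SAP 3.5.2.1 uses the Overall Safety Population for unsolicited data after any vaccination. A reader might also infer three incompatible windows, but the day counts show that two of the three nearly coincide.

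The *last* dose phrase can also be read as stating how long follow-up continues. The SAE endpoint has the same form (180 days after the last dose), while Protocol 9.4 starts SAE observation at consent and ends AE observation 28 days after the last vaccination. Protocol 1.3 already describes "unsolicited adverse events for at least 28 days following the last study vaccination dose". All of this stands, although the parenthesis in 4.13 makes the follow-up reading less natural.

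On by-dose tables, Protocol 11.3.2.2 says of the unsolicited summaries "All summaries will be presented by treatment group overall and by age stratum" and names none by dose. They are implied by the endpoint rather than promised in a table list. The change is declared openly. Dose number follows from age and vaccination history, not from the assigned vaccine, so pooling should not bias the comparison between arms in expectation. These points limit the weight of the finding. They do not reconcile 4.13 with 2.2.2, 4.7.4 and 4.7.4.4, and they do not make the per-dose endpoint readable.

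**Conclusion.** The point holds as a minor one about wording and presentation. The endpoint text in SAP 4.13 conflicts with SAP 2.2.2 and 4.7.4 and does not describe the rule in 4.7.4.4. The protocol's per-dose unsolicited AE endpoint cannot be read from the planned tables, which combine follow-up differing by a factor of two.

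No events are planned to be deleted, no between-arm bias is shown, and the primary immunogenicity analysis is untouched. The day counts assume visits within the stated windows. How much the pooling changes any reported percentage is unknown, because it depends on the share of two-dose children and on when events occur, and the documents give neither.

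**What to change.** Replace the reworded endpoint in SAP 4.13 with one window: first vaccination through the Exit Visit, which for two-dose children is the visit after dose 2. Use it in 2.2.2, 4.7.4 and 4.7.4.4. In 4.7.4.4, qualify the Day 29 + 4 gloss on the exit visit: counted from dose 1, that is the second-vaccination visit for a two-dose child.

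Add a summary of unsolicited AEs after dose 1 and after dose 2, by arm and age stratum. Use children who received dose 2 as the denominator for the second period, and state a rule for events starting on the day of dose 2.

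The cost is SAP wording and a few extra tables from onset dates already collected. No new visits, data or subjects are needed.

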### 4.14 Algorithms/SAS Codes

- **Tables that need descriptive statistics – continuous variables:**

[REDACTED]

- **Tables that need frequency counts:**

[REDACTED]

- **Tables that need exact 95% CIs between groups for proportions::**

[REDACTED]

**Notes:** 1 Estimates are computed for 2x2 tables only

2 This code also gives exact 95% CIs within group for binomial proportions

- **Tables that need 95% CIs within group for binomial proportions:**

[REDACTED]

- **Code to create 95% CIs within group for continuous variables:**

[Redacted code]

- **Tables that need exact 95% CIs for relative risk, risk difference and Cochran Mantel Haenszel Statistics:**

[Redacted code]

**Notes:** Estimates are computed for 2x2 tables only

- **Tables that require analysis of (co)variance and 95% CIs between arms for continuous variables:**

[Redacted code]

**Note:** (Treatment order: 1=drug 1,2= drug 2)

- **The geometric mean is the antilog of the arithmetic mean of the logs:**

[Redacted code]

## 5 Tables and Listings

### 5.1 Table Format

All output will be produced using SAS version 9.2 or a later version.

In the top left portion of each table/listing, a *table/listing number* followed by the *title* of the table/listing will be presented. After the title line, optional *sub-title* or *population* information can be presented. Horizontal lines will appear before and after the column heading of the table/listing. *Footnotes* will be put under the main body of text at the bottom of the page.

The *sponsor name*, *protocol number*, programmers User ID, status of the table/listing (i.e. draft or final) and *SAS program name* will appear bottom left in a string and the *page number* will appear on the bottom right corner of each table/listing. The *date and time of creation* of table/listing will appear bottom left under the sponsor name. The source listing number will appear bottom left.

A *landscape layout* is proposed for both table and listing presentations.

The *left* and *right margins* of all tables and listings will be a minimum of 2.1 cm from the left and 1.9cm from the right. The *top and bottom margins* will be a minimum 2.92cm. *Header and footer* will be both 1.27 cm.

There is no special requirement of *font type* and *size*, but an *8-point* font size for tables and *7* or *8-point* for listings is proposed using *Courier New* font. A maximum SAS line size=141 and page size=44 for *8-point* font size, and line size=161 and page size=50 for *7-point* will be used so as to fit on both UK and US paper sizes.

In a listing, in the case that a subject's record has been continued to the next page, an appropriate identification (e.g., the subject ID number) must be presented at the beginning of that page.

